## LIST OF ABBREVIATIONS

Abbreviation	Explanation
Aqueous-PREP	A Pragmatic Randomized trial Evaluating Pre-operative aqueous antiseptic skin solutions in open fractures
CDC	Centers for Disease Control and Prevention
CEO	Center for Evidence-Based Orthopaedics
CHG	Chlorhexidine gluconate
CI	Confidence interval
CRF	Case report form
EDC	Electronic data capture
FDA	Food and Drug Administration
FLOW	Fluid Lavage of Open Wounds trial
FRI	Fracture-related infection
GEE	Generalized estimating equations
HRPO	Human Research Protection Office
ITT	Intention-to-treat
IRB	Institutional Review Board
ORP	Office of Research Protections
REB	Research Ethics Board
SAE	Serious adverse event
SSI	Surgical site infection
USAMRMC	United States Army Medical Research and Materiel Command

## STUDY SUMMARY

Methodology	Cluster randomized crossover design.
Coordinating Center	This study will be centrally coordinated by the Methods Center at the Center for Evidence-Based Orthopaedics (CEO), McMaster University, Hamilton, Ontario and by the Administrative Center within the Department of Orthopaedics at the University of Maryland, R Adams Cowley Shock Trauma Center, Baltimore, Maryland.
Clinical Sites	At least 12 clinical sites. Additional clinical sites will be included or removed as needed.
Background	The prevention of infection is the single most important goal influencing peri-operative care of patients with open fractures. Standard practice in the management of open fractures includes sterile technique and pre-operative skin preparation with an antiseptic solution. The available solutions kill bacteria and decrease the quantity of native skin flora, thereby decreasing surgical site infection (SSI).  While there is extensive guidance on specific procedures for prophylactic antibiotic use and standards for sterile technique, the evidence regarding the choice of antiseptic skin preparation solution is very limited for open fracture surgery.
Objectives	The overall objective is to compare the effectiveness of aqueous pre- operative antiseptic skin preparation with 10% povidone-iodine versus 4% chlorhexidine gluconate (CHG) for the management of open fractures. A ranked order for assessing effectiveness will be used with surgical site infection (SSI) as the primary comparison and unplanned fracture-related reoperations as the secondary comparison.
Subgroup Objectives	We will explore if the pre-operative antiseptic skin solutions have different magnitudes of effect on SSI within three clinically important open fracture subgroups: severity of open fracture, location of fracture, and severity of wound contamination.
Diagnosis and Main Inclusion Criteria	All patients 18 years of age or older who present to a recruiting hospital for treatment of an open fracture(s) of the appendicular skeleton will be screened for participation within 3 weeks of their fracture. Eligible patients must receive surgical debridement of their open fracture wound(s) within 72 hours of their injury and the open fracture(s) must be managed definitively with a surgical implant (e.g., internal fixation, external fixation, joint prosthesis, etc.).

Treatment Groups	The Aqueous-PREP trial will compare two common iodophor and chlorhexidine based pre-operative antiseptic skin solutions used during open fracture surgery: 1) Povidone-iodine : 10% povidone-iodine (1% free iodine) in purified water and 2) CHG : 4% chlorhexidine gluconate in purified water.	
Randomization	Treatment allocation will be determined using a cluster-randomized crossover trial design. The order of treatment allocation for each orthopaedic practice will be randomly assigned using a computer-generated randomization table. Each site will start with the initially allocated study solution and eventually crossover to the other solution for their second recruitment period. This process of alternating treatments will repeat approximately every 2 months as dictated by the initial randomization.	
Study Outcomes	The primary outcome is SSI, guided by the Centers for Disease Control and Prevention's (CDC) National Healthcare Safety Network reporting criteria,  which includes superficial incisional SSI within 30 days and deep incisional or organ/space SSI within 90 days of definitive fracture management surgery. The secondary outcome is the occurrence of an unplanned fracture-related reoperation within 12 months of the fracture. Alternative definitions of SSI, including the confirmatory criteria for Fracture-Related Infection (FRI) and the CDC criteria within 1 year of injury will be used for sensitivity analyses of the primary comparison. All study outcomes will be adjudicated by a blinded committee using clinical notes and radiographs.	
Follow-Up	Study participants will be followed at 6 weeks, 3 months, 6 months, 9 months, and 12 months from their fracture.	
Sample Size	A minimum of 1,540 participants with open fractures.	
Significance	SSIs are often devastating complications for open fracture patients because of the resultant reoperations, adverse events from antibiotic courses, and fracture healing difficulties. Given the severity of open fractures, maximizing the effectiveness of current prophylactic procedures is essential. The Aqueous-PREP trial will provide necessary evidence to guide the prevention of SSIs in open fractures, and the trial is poised to have a significant impact on the care and outcomes of open extremity fracture patients.	

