#### 3.0 TRIAL DESIGN

#### 3.1 Summary

This study is a multi-center pragmatic cluster randomized crossover trial of a minimum of 1,540 participants with open extremity fractures requiring surgical management. The unit of randomization is the orthopaedic practices within clinical sites (clusters), with individual patients being the unit of analysis. Recruitment for each treatment group will be performed in multiple iterations of approximately two-month periods. Each orthopaedic practice will initially be randomized to use one of two pre-operative aqueous surgical skin preparation solutions (10% povidone-iodine or 4% CHG) for open fracture surgeries at their institution (Figure 1). Upon completion of the two-month period, each orthopaedic practice will crossover to the alternative treatment allocation and complete another two-month recruitment period. This process of alternating treatment periods (crossovers) will continue until the minimum sample size is achieved and the study's budgeted recruitment duration is completed. Upon completion of recruitment, it is expected that each orthopaedic practice will enroll a minimum of 77 patients per treatment, and that most clinical sites will exceed this minimum recruitment goal. Clinical site personnel will screen potential patients for eligibility, and if eligible, they will be invited to participate in the trial. Study participants will be assessed at regular intervals in the one year following their fracture. The primary outcome will include any SSI event from the time of open fracture to the end of the 30and 90-day post-operative periods from their definitive fracture management surgery. The secondary outcome will include unplanned fracture-related reoperations that occur within one-year of their fracture. A blinded Adjudication Committee will review SSIs and unplanned fracturerelated reoperations to confirm that they meet the criteria for being a study event.

[figure not shown]

Figure 1: Randomized Treatment Allocation, Cluster Crossover, and Recruitment

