## 4.5 Blinding

The orthopaedic team (including the study coordinators) cannot be blinded to the treatment allocation as the antiseptic solutions are visually distinguishable and these individuals need to lead the implementation of the cluster-crossover protocol at their clinical site. The Adjudication Committee Members and data analysts will be blinded to the study treatment. All interpretation of study results will initially be done in a blinded manner by developing two interpretations of the results. One interpretation will assume treatment A is povidone-iodine, the other interpretation will assume it is CHG. Once the data interpretations for each assumption are finalized, the data will be unblinded and the correct interpretation will be accepted.

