## 4.8 Outcome Measures

#### 4.8.1 Primary Outcome

The primary outcome is SSI, guided by the CDC's National Healthcare Safety Network reporting criteria (2017), which includes superficial incisional SSI within 30 days and deep incisional or organ/space SSI within 90 days of fracture surgery (**Table 3**). Since the management of some open fractures may have more than one operative procedure as part of an intentionally staged surgical plan (e.g., multiple irrigation and debridements, wound closures, temporary stabilization surgeries, definitive fixation surgery), the primary outcome will include any SSI event from the date of open fracture to the end of the 30- and 90-day post-operative surveillance periods from their definitive

fracture management surgery. For participants with multiple open fracture regions, the date of the definitive fracture management surgery will be matched to the open fracture region with the SSI.

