## 4.8.2 Secondary Outcome

The secondary outcome is unplanned fracture-related reoperation within 12 months of the open fracture. This outcome has been used in previous open fracture trials and is defined as any unplanned surgery that occurred from the time of injury to 12 months post-injury that is associated with an infection at the operative site or contiguous to it, a wound-healing problem, or a fracture delayed union or nonunion. Common examples include any unplanned: 1) irrigation and

debridement of surgical incisions or open fracture wounds due to infections or wound healing problems; 2) revision wound closure for dehiscence; 3) soft tissue coverage procedure for infected or necrotic wound; 4) fracture delayed union or nonunion surgery (such as bone grafting or implant exchange); and 5) reoperation for hardware or prosthesis failure due to infection or bone-healing problems. Removal of hardware for soft tissue prominence or periprosthetic fracture are common examples of reoperations that will not be considered outcome events. Two orthopaedic surgeons who are members of the Adjudication Committee will independently review all reported unplanned fracture-related reoperations to determine if they meet the criteria for being a study event. The Committee will reach consensus on all reviewed unplanned fracture-related reoperations.

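### Blinded adjudication of unplanned reoperation works in one direction: the committee can reject a reported event but has no described route to recover one that the unblinded site classed as planned

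*Combined protocol and SAP*

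**What the plan says.** The Study Summary gives a general assurance: "All study outcomes will be adjudicated by a blinded committee using clinical notes and radiographs".

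Section 4.8.2 defines the secondary outcome by two conditions. The surgery must be unplanned, and it must be linked to infection at or next to the operative site, a wound-healing problem, or delayed union or nonunion. The window runs from injury to 12 months. Hardware removal for prominence is named as a non-event. Two orthopaedic surgeons on the Adjudication Committee "independently review all reported unplanned fracture-related reoperations to determine if they meet the criteria for being a study event". Section 3.1 describes the committee's task in the same way: it reviews the cases "to confirm that they meet the criteria for being a study event".

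Section 4.8.4 has site personnel identify reoperations when they occur or at clinic visits and record review, and record the date, type and reason. Section 4.5 says of those personnel: "The orthopaedic team (including the study coordinators) cannot be blinded to the treatment allocation as the antiseptic solutions are visually distinguishable". The committee itself is masked: "The Adjudication Committee Members and data analysts will be blinded to the study treatment".

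Section 4.8.1 recognises that open fractures may be treated "as part of an intentionally staged surgical plan (e.g., multiple irrigation and debridements, wound closures, temporary stabilization surgeries, definitive fixation surgery". Section 4.8.4 also has sites record the use of staged debridements for each fracture region.

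**The concern.** A reader of the summary would take it that blinded surgeons decide which operations count as reoperation events. Under section 4.8.2 they decide only among operations that the site has already reported as unplanned. That first sort is made by people who know which solution was used.

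The outcome window opens at injury, so it includes the phase in which staged debridement and closure are ordinary care. The plan gives no working definition of unplanned, and it does not require the staged plan to be written down before the next operation. If labelling shifts even slightly with the solution in use, the trial's only secondary outcome is biased, and masked review downstream cannot put the missing events back. The crossover design removes a labelling habit that is constant within a site. It does not remove one that changes with the solution.

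**Working it through.** **Route of a case to the committee**

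| Return to surgery | Described route to blinded review | Can the committee correct the site? |
|---|---|---|
| Reported as unplanned and fracture-related | Yes (3.1, 4.8.2) | Yes, it can reject the event |
| Called planned or staged, infection reported as SSI | Through SSI review (4.8.1, 4.8.3) | Partly: the infection is reviewed, but the text does not say that reoperation status is then decided |
| Called planned or staged, wound-healing or bone-healing problem without a reported SSI | None found | No |
| Attributed to an excluded reason such as prominent hardware, no reported SSI | None found | No |

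**Where the label decides.** The staged procedures named in 4.8.1 are debridements, closures, temporary stabilization and definitive fixation. The event examples in 4.8.2 include debridement for infection or wound problems and repeat closure after dehiscence. The two lists meet at repeat debridement and wound closure. There, a second operation with a qualifying or arguable cause is an event if called unplanned and a non-event if called planned.

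**Illustration of consequence.** The plan has no figure of its own to reproduce here. Inputs:

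- Reoperation risk p = 0.13 (section 5.1).
- Analysed per group: 1,540 × 0.90 / 2 = 693 (section 5.1, minimum enrolment and 10% loss).
- Two-sided test at 0.05 (Table 5; section 5.2.1 gives two-sided intervals).
- No true effect. A share m of one group's qualifying events is labelled planned. **The values of m are assumptions; the documents give none.**
- Clustering is ignored.

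Expected events per group: 693 × 0.13 = 90.1. The apparent risk ratio is 1 − m.

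With a = 0.13, b = 0.13(1 − m), d = a − b and p̄ = (a + b)/2:

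- SE0 = √[2p̄(1 − p̄)/693]
- SE1 = √[(a(1 − a) + b(1 − b))/693]
- Rejection rate = 1 − Φ[(1.96·SE0 − d)/SE1] + Φ[(−1.96·SE0 − d)/SE1]

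For m = 0.10: b = 0.117, d = 0.013, p̄ = 0.1235, and SE0 and SE1 are both 0.01767. The arguments are 1.225 and −2.696, and the rejection rate is 0.114.

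| m | Hidden events | Apparent RR | Rejection rate |
|---|---|---|---|
| 0 | 0 | 1.00 | 5.0% |
| 5% | 4.5 | 0.95 | 6.5% |
| 10% | 9.0 | 0.90 | 11.4% |
| 15% | 13.5 | 0.85 | 20% |

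With 700 per group (half of Table 5's 1,400), the three non-zero rows give 6.5%, 11.5% and 20.2%.

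If the same share is hidden in both groups, the cost is power. With 700 per group and a true risk ratio of 0.65, power falls from 78.6% to 73.8% at m = 10%, 68.2% at 20% and 61.9% at 30%.

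**The case against.** Much can be said for the plan.

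- **The label is not the whole definition.** A reader might infer that planned versus unplanned alone separates an event from staged care. Section 4.8.2 does not support that: a routine second-look debridement with no qualifying cause is a non-event whatever it is called. This stands and limits the problem to cases where such a cause is present or arguable.
- **The overlap is limited.** A reader might extend it to soft tissue coverage and bone grafting. Section 4.8.1 names neither among its staged procedures. This stands.
- **There is a second route.** All reported SSIs go to masked review and are also judged against the fracture-related infection and 12-month CDC criteria (4.8.1, 4.8.3). It would be wrong to say the committee never sees an operation labelled planned. But this route also depends on site reporting, and it does not help wound-healing or nonunion cases without a reported infection.
- **Some signal exists.** The 12-month infection analyses in 5.2.4 do not use the label, so a treatment difference there without one in reoperation would be a partial warning. None of the listed sensitivity analyses addresses ascertainment of reoperations directly.
- **Planned status is used before surgery.** Section 4.6.2 keeps the allocated solution for planned repeat operations after a site crosses over, so near a crossover, sites need to know in advance which operations are planned. This limits after-the-fact labelling but is not a documentation rule.
- **No direction is shown.** Section 1.7 reports surgeons split almost evenly between solutions, and it describes an earlier trial and a survey, not this trial's surgeons. Opposing preferences could partly cancel. This stands.

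**Conclusion.** For the secondary outcome, masked review can remove events but not restore them, apart from infections separately reported as SSIs. That follows from sections 4.8.2, 4.8.4 and 4.5 read together. The summary sentence is incomplete on this point. A reader might call it contradicted, but adjudicating what sites report is compatible with it, and sections 3.1 and 4.8.2 say openly that this is what happens.

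A reader might also take the rejection rates of about 6.5%, 11% and 20% as an estimate of bias. They are not. They rest on assumed one-group mislabelling of 5%, 10% and 15%, on the plan's 13% risk, and on a simple two-group test. They show only that roughly 5 to 14 hidden events out of about 90 would be enough to matter. The real rate and its direction are unknown, and the plan as written would not measure them.

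The primary outcome also relies on site reporting, but not on the planned or unplanned label, so this point does not reach it. The change is a worthwhile, inexpensive improvement to the secondary outcome.

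**What to change.** In section 4.8.2, replace the review trigger. Send to the existing blinded two-surgeon panel, whatever the site's label or stated reason:

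1. every return to surgery on a study fracture region after the definitive fracture management surgery; and
2. every earlier repeat procedure for which the site records infection, a wound-healing problem or a bone-healing problem.

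Add a random sample of the remaining procedures labelled planned, as a check on what the trigger misses. Give the panel the dated operative notes with the solution masked, and let it decide planned versus unplanned. Report by group how many returns to surgery were classed as planned.

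The trigger should not rest on whether an operation appears on a plan written by the treating surgeon. That surgeon is unblinded, and an open-ended plan for further debridement would exempt later operations from review.

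The cost is additional reviews by the panel, including preparation of masked notes. Reoperation data are already scheduled at every visit (Table 2), with date, type and reason recorded (4.8.4). No new staff, visit or patient procedure is needed.

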#### 1.0 INTRODUCTION

## 1.1 Open Fractures

Open fractures represent some of the most severe musculoskeletal injuries. Due to their highenergy mechanisms, these extremity fractures are accompanied by soft-tissue injuries that contribute to unacceptably poor outcomes. The Fluid Lavage of Open Wounds (FLOW) trial of 2,447 open fracture patients reported a 13.2% incidence of open fracture-related reoperations;  however, these study events were even more common in open wounds with severe contamination (29.8%, 95% confidence interval (CI): 22.6–38.1%) and in patients with higher grades of injury (Gustilo-Anderson Type III: 18.0%, 95% CI: 15.6–20.7%). Ultimately, complications from open fractures lead to prolonged morbidity, loss of function, and potential limb loss.

## 1.2 Prevention of Infection

The prevention of infection is the single most important goal influencing peri-operative care of patients with open fractures. Standard practice in the management of open fractures includes sterile technique and pre-operative skin cleaning with an antiseptic solution. The available solutions kill bacteria and decrease the quantity of native skin flora, thereby decreasing surgical site infection (SSI). While there is extensive guidance on specific procedures for prophylactic antibiotic use and standards for sterile technique, the evidence regarding the choice of antiseptic skin preparation solution is very limited for open fracture surgery.

## 1.3 Rationale for Pre-Operative Antiseptic Skin Solution Prophylaxis

The most common skin preparation solutions include either an iodophor or chlorhexidine-based active ingredient, and are delivered in an alcohol or aqueous-based solution. Iodophors achieve effective antisepsis by penetrating the cell wall of microorganisms and disrupting critical protein and nucleic acid structures. Iodophors are effective against most bacteria, but also may have broader-spectrum coverage of mycobacteria, viruses, and some spores compared to chlorhexidine gluconate (CHG). CHG similarly achieves antimicrobial effects by penetrating the cell wall of microorganisms. This antimicrobial action allows CHG to be effective against most bacteria.

The evidence guiding pre-operative antiseptic skin solution choice in fracture surgery is largely extrapolated from other surgical disciplines. In a randomized controlled trial involving 849 patients undergoing clean-contaminated abdominal, gynecologic, or urologic surgery, the use of 2% CHG in 70% isopropyl alcohol was compared to aqueous 10% povidone-iodine. The overall rate of 30-day SSI was significantly lower in the CHG-alcohol group than the povidone-iodine group (9.5% vs. 16.1%; P=0.004; relative risk, 0.59; 95% CI: 0.41–0.85). While this study demonstrated superior efficacy of CHG-alcohol compared to povidone-iodine, comparing an alcohol based solution to an aqueous solution creates uncertainty about whether the result observed occurred from the superiority of CHG over iodine, isopropyl alcohol over water, or a synergistic combination of CHG with alcohol. In an effort to overcome the controversies associated with comparing CHG and iodine in different solutions, a more recent randomized controlled trial of 1,147 caesarean section patients allocated patients to 2% CHG with 70% isopropyl alcohol versus 8.3% povidone-iodine with 72.5% isopropyl alcohol. Similar to the previous randomized controlled trial, CHG proved more efficacious for reducing 30-day SSI (4.0% in the CHG-alcohol group and 7.3% in the iodine-alcohol group; relative risk, 0.55; 95% CI: 0.34–0.90; P=0.02).

While the evidence from the above two randomized controlled trials demonstrate decreased SSI from CHG solutions in clean-contaminated abdominal and genito-urinary surgery, a larger nonrandomized trial reported opposite effectiveness results. Swenson et al., completed a larger 3,209 patient pragmatic sequential implementation study, in which the use of the preoperative skin antiseptic solution was changed after six-month periods. In this study, there were three treatment periods, each with approximately 1,000 general surgery patients undergoing elective and emergent cases. In the first period, patients received 7.5% povidone-iodine scrub, 70% isopropyl alcohol scrub, and 10% povidone-iodine skin paint. The second group received 2% CHG with 70% isopropyl alcohol (CHG group), and the third group received 0.7% iodine povacrylex in 74% isopropyl alcohol. Adjusted comparisons were performed using the intention to treat principle and an as-treated analysis. Lower SSI rates were seen in the povidone-iodine skin paint group (4.8%) and the iodine povacrylex in isopropyl alcohol group (4.8%), compared with the SSI rates in the 2% chlorhexidine and 70% isopropyl alcohol group (8.2%) (P< 0.05; povidone-iodine skin paint odds ratio: 0.56, 95% CI: 0.40-0.79).4 While the results of the Swenson study contradict those of the smaller randomized controlled trials, this large pragmatic study further highlights that the choice of antiseptic skin solution affects SSIs, and data to select the best solution remains conflicting.

Considering the conflicting data, the most recent Cochrane systematic review comparing the efficacy of pre-operative antiseptic skin solutions for clean surgery concluded, "investment in at least one large trial (in terms of participants) is warranted to add definitive and hopefully conclusive data to the current evidence base. Ideally any future trial would evaluate the iodine-containing and chlorhexidine-containing solutions relevant to current practice..." The Cochrane recommendation is a direct response to the limitations of the current available literature comparing antiseptic skin solutions. For orthopaedic fracture surgery, the impact of the treatment uncertainty is further magnified when considering the higher rates of SSIs among open fracture patients.

1.4 Extrapolating Evidence from Other Surgical Disciplines to Fracture Surgery is Problematic With regards to orthopaedic patients, the inconsistent results leave the optimal antiseptic solution in doubt; in addition, results may differ across surgical settings. The risk of SSI is substantially greater in open fracture patients due to both the nature of the injury and the required surgery to fix broken bones. Furthermore, the emergent nature of fracture surgery means that patients are unable to undergo other prophylactic skin care, such as CHG bathing, which is rendered to elective cases to reduce SSI.

Most important, the contamination from the injury is a critical difference from elective abdominal or gynecologic surgery. Other differences include substantial soft tissue damage during the injury, the use of a tourniquet that decreases the blood flow to the limb (potentially increasing the risk of infection), and the additional risk of implanting metal fixation that can harbor bacteria. Swenson *et al.*, directly acknowledged that the studies performed in general surgery patients may not apply to other specialties, particularly orthopaedic surgery. Even if one wanted to directly apply the conflicting results outlined above to the care of open fractures, there are critical limitations in the sparse general surgery and obstetrical literature available.

The most significant limitation in the existing literature is the use of a 30-day endpoint for SSI in all three studies described above. 1,2,4 While this may be acceptable for identifying most SSIs that

involve only the skin (superficial SSI), infections that occur deep to the muscle and around the bone (deep SSI and organ/space SSI) often present beyond 30-days post-injury and have significantly more morbidity and mortality than superficial SSI. This is a major limitation to the external validity of the previous studies' ability to guide fracture fixation practice. In the FLOW open fracture trial, nearly half the infection-related complications were identified between 30 and 90 days from injury. Not only does the existing literature not extend follow-up during this period, it is plausible that the treatment effects of the antiseptic solutions behave differently for preventing deep or organ/space infections that often present between 30 and 90 days post-surgery. The need for longer follow-up is supported by a mandatory 90-day surveillance period for deep and organ/space SSIs according to the Centers for Disease Control and Prevention (CDC). Therefore, the lack of directly applicable evidence, an overall paucity of good clinical evidence, and the inadequate duration of outcome follow-up mandate the need for a large, rigorous clinical trial in surgical preparation solutions in open fracture care.

